12.4. Severity of Adverse Events

Each AE will be assessed for its severity or for its intensity as experienced by the subject and according to the most recent MedDRA Version.

- **Grade 1 – Mild**
- **Grade 2 – Moderate**
- **Grade 3 – Severe**
- **Grade 4 – Life Threatening**
- **Grade 5 – Death**

12.5. Adverse Events Outcomes

The Investigator will categorize the outcome of AEs according to the definitions below:

- **Resolved:** The subject recovered from the AE.
- **Not Resolved/Ongoing:** At the time of the last assessment, the event is ongoing, with an undetermined outcome. Note: Ongoing AEs are not considered resolved as a result of death. No AE stop date will be recorded with an AE that is ongoing.

- **Chronic/Stable:** At the time of the last assessment, the event is ongoing and stabilized, with no change to the event outcome anticipated.
- **Death:** The AE directly caused death.
- **Unknown:** There is an inability to access the subject or the subject's records to determine the outcome (i.e., subject withdraws consent or is lost to follow-up).

12.6. Serious Adverse Events

An SAE or reaction is any untoward medical occurrence that at any dose:

- Requires inpatient hospitalization or prolongation of existing hospitalization
- Results in persistent or significant disability or incapacity
- Is a congenital anomaly or congenital disability
- Is a significant medical event (e.g., intensive treatment in an emergency room or for allergic bronchospasm; blood dyscrasias, or convulsions that do not result in hospitalization; or development of drug dependency or drug abuse; malignancy)
- Is life-threatening
- Results in death

12.7. Abnormal Laboratory Values

Any abnormality in a laboratory value that is new in onset, or which has worsened in severity or frequency from the baseline condition and meets 1 of the following criteria will be recorded on the AE pages of the eCRF:

- Is judged by the investigator as clinically significant
- Leads to discontinuation of the investigational product
- Requires therapeutic intervention or diagnostic tests
- Has accompanying or inducing symptoms or signs

12.8. Pregnancy

The Sponsor should report all pregnancies and pregnancies in the partners of subjects to the REB/IRB and Regulatory Authorities per institutional and/or regulatory guidelines.

Women who become pregnant during the study will be immediately discontinued from the study; if the woman was taking a double-blind treatment, the blind will be broken to determine whether the woman was taking placebo or FSD201; in the latter case, the woman will be regularly followed during the pregnancy until the child is born. Male participants whose partners become pregnant during the study will be immediately discontinued from the study; if the man was taking a double-blind treatment, the blind will be broken to determine whether he was taking placebo or FSD201.

Subjects should be instructed to immediately notify the investigator of any pregnancies and the investigator should counsel the subject, discussing any risks of continuing the pregnancy and any possible effects on the fetus.

A Pregnancy Reporting Form should be completed by the investigator and submitted to Ozmosis Research Inc. either by email ([contact]) or via [contact]) within 24 hours after learning of the pregnancy. Pregnancy should not be recorded on the Adverse Event eCRF but the date of pregnancy will be recorded in the database on the Pregnancy Report form CRF.

13. Reporting Procedures and Requirements

Any Adverse Events (AEs) occurring before the start of treatment (i.e., before the first dose of the investigational product) will be recorded in the medical history. The AE reporting period for this study begins when the subject received the first dose of study drug on trial and ends at the last follow-up visit. All AEs must be recorded in the eCRFs. The sign, symptoms, or diseases present before starting the treatment period are only considered AEs if they worsen after starting the treatment period.

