11. Female subjects of childbearing potential must use an acceptable method of birth control. Acceptable birth control includes total abstinence from heterosexual intercourse, a vasectomized partner, intrauterine device, or double barrier method including condoms, sponge, diaphragm, contraceptives (oral, parenteral, or transdermal), or vaginal ring with spermicidal jellies or cream. Subjects considered not of childbearing potential must be surgically sterile (total hysterectomy, bilateral salpingo-oophorectomy, or tubal ligation) or be more than one year post-menopausal, defined as a complete cessation of menstruation for at least one year. Male subjects who are sexually active must use an acceptable method of birth control. Acceptable birth control includes total abstinence from heterosexual intercourse, or use of a double barrier method including condoms sponge, diaphragm, contraceptives (oral, parenteral, or transdermal), or vaginal ring with spermicidal jellies or cream used by partner. Periodic abstinence and withdrawal are not acceptable methods of contraception.
12. The subject is in good health as judged by the investigator, based on medical history, physical examination, serum chemistry, hematology, and urine analysis

13. At the screening visit, the body mass index (BMI) is between 18 and 39 kg/m²
14. The subject is sufficiently fluent in English language to answer the questionnaires in clinic and on the App.

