14. Positive urine drug screen for illegal or non-prescribed drugs at the Screening Visit or during the treatment period
15. Pregnant or lactating females or females planning to become pregnant during the study or within 28 days following the last dose of study medication
16. Male patients planning a partner pregnancy or sperm donation during the study or within three months following the last dose of study medication
17. Patients with active malignancy or history of malignancy, except for basal cell or squamous cell carcinoma and actinic keratosis. Basal cell carcinoma and small squamous cell carcinoma of the skin which have been excised according to guidelines within the last 5 years or in situ cervical carcinoma that has been fully treated and shows no evidence of recurrence are allowed
18. Positive human immunodeficiency virus (HIV), hepatitis B or hepatitis C laboratory result
19. Any clinically significant unstable medical abnormality or acute or chronic disease of the cardiovascular, gastrointestinal, respiratory, hepatic, or renal systems. Subject with aspartate transferase or alanine transferase > 2.5 times the upper limit of normal (ULN) or alkaline phosphatase > 3.0 times ULN
20. Any clinically significant deviation from normal in physical examination, vital signs, or clinical laboratory tests, as determined by the investigator
21. Known history of seizure disorder, epilepsy, convulsions, or increased intracranial pressure anytime during the subject's life except for pediatric febrile seizures
22. Subject has received an investigational therapy of any kind within 28 days or 5 half-lives, whichever is longer, before Screening Visit
23. Subject has had known hypersensitivity or intolerance to the use of PEA, diphenhydramine (e.g. Benadryl) or acetaminophen (e.g. Tylenol) and/or their associated formulation components
24. The subject is a member of the site staff or relative of a staff member
25. Individuals with high baseline serum tryptase levels suggestive of Primary or Secondary MCAS (defined as above the normal range of 2.2 to 13.2 µg/L)

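### Inclusion 11 sets no post-dose contraception period to match exclusions 15 and 16, and section 12.8 requires no outcome follow-up for partners of men on FSD201

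*Combined protocol and SAP*

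**What the plan says.** **Contraception.** Inclusion 11 (section 10.1, repeated in the synopsis) states "Female subjects of childbearing potential must use an acceptable method of birth control" and "Male subjects who are sexually active must use an acceptable method of birth control". It lists acceptable methods but gives no end date.

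**Planning exclusions.** Section 10.3 excludes, under no. 15, "Pregnant or lactating females or females planning to become pregnant during the study or within 28 days following the last dose of study medication" and, under no. 16, "Male patients planning a partner pregnancy or sperm donation during the study or within three months following the last dose of study medication".

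**Checks during the study.** Table 1 schedules a review of the eligibility criteria and a pregnancy test at screening, Days 0, 14, 28 and 56, and Early Termination. Visit 11 (Day 63) is a phone call with neither.

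**Pregnancy.** Section 12.8 says "Subjects should be instructed to immediately notify the investigator of any pregnancies", requires a reporting form within 24 hours, and adds "The Sponsor should report all pregnancies and pregnancies in the partners of subjects to the REB/IRB and Regulatory Authorities". A woman who conceives on study is discontinued and unblinded. If she was on FSD201, "in the latter case, the woman will be regularly followed during the pregnancy until the child is born". For men it says "Male participants whose partners become pregnant during the study will be immediately discontinued from the study", followed by unblinding and nothing further. Section 7.1.3 justifies withdrawal and unblinding in both cases by fetal risks that are not known.

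**SAEs.** Section 12.6 counts a congenital anomaly as an SAE. Section 13.1 runs SAE reporting from first dose to the last follow-up visit. Sections 6.2 and 8.2.3 say that SAEs up to 7 days after the last intake are collected. Section 13.2 gives no cut-off for expedited reports to authorities.

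**The concern.** Exclusions 15 and 16 ask only about intentions. A subject with no plan to conceive passes both, and nothing in inclusion 11 stops that subject from giving up contraception at the last dose. The sponsor evidently regards the 28 days and three months as relevant, yet no rule covers unplanned conception in them.

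On partners, breaking the blind shows whether the father took FSD201, but the protocol then requires nothing about how the pregnancy ended. With fetal risk described as unknown, each exposed pregnancy is scarce safety information and hard to recover later. At stake are subject and fetal safety and the completeness of the safety record, not the efficacy result.

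**Working it through.** **1. Timeline.** The plan's own figure reproduces: 17 days screening + 56 treatment + 7 follow-up = 80 days (sections 6.1 and 8.2.3).

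**2. Post-dose periods.** Take the last dose on Day 56 and three calendar months as 89 to 92 days (assumption).
- Women: 56 + 28 = Day 84.
- Men: 56 + 89 = Day 145 to 56 + 92 = Day 148.

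The last criteria review and pregnancy test for a completer fall at Visit 10 (Day 56).

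**3. Time inside those periods with no stated contraception rule.** Inclusion 11 gives no end, so the answer depends on how it is read. Visit 11 comes 7 ± 2, that is 5 to 9, days after the last dose (8.2.3). Early Termination comes up to 14 + 2 = 16 days after discontinuation (7.1.7; last dose assumed on that day).

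| Requirement read as lasting to | Women | Men |
|---|---|---|
| Last dose | 28 − 0 = 28 days | 89 to 92 days |
| Visit 11 call | 28 − 9 = 19 to 28 − 5 = 23 days | 89 − 9 = 80 to 92 − 5 = 87 days |
| Latest Early Termination visit | at least 28 − 16 = 12 days | at least 89 − 16 = 73 days |

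No reading reaches zero. These are lengths of time without a rule, not measures of risk.

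**4. Outcome follow-up in 12.8, side by side.**

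| | Woman on FSD201 | Partner of man on FSD201 |
|---|---|---|
| Pregnancy notified and reported | yes | yes |
| Subject discontinued and unblinded | yes | yes |
| Pregnancy followed to birth | yes | not stated |

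At most the roughly 40 subjects on FSD201 (section 10.5) are concerned.

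The follow-up of women is also tied to pregnancy occurring on study. If that means the woman's own participation, as the 80-day maximum and the immediate discontinuation suggest, conception after her Visit 11 call but within 28 days is not covered. If it means the overall study end in 15.1, only women whose last dose falls in the final 28 days of the study are affected.

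**5. SAE period (secondary).** Visit 10 may fall at 56 + 2 = Day 58, so the follow-up call is at the latest 58 + 7 + 2 = Day 67. A late Early Termination visit gives 58 + 16 = Day 74. For conception on Day 0, assume birth 154 days (22 weeks) to 266 days (38 weeks) later.
- From Day 67: 154 − 67 = 87 to 266 − 67 = 199 days after the cut-off.
- From Day 74: 154 − 74 = 80 to 266 − 74 = 192 days after it.

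If the last follow-up visit in 13.1 means the scheduled one, a birth conceived on study falls outside the period. If it includes the pregnancy follow-up ordered by 12.8, the birth falls inside for a woman on FSD201. The text does not say which.

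**The case against.** Several points on the other side stand.

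- Eligibility criteria and pregnancy status are reviewed again at Day 56 or Early Termination, so current contraception and plans to conceive are rechecked as dosing ends. That narrows the gap to unplanned conception afterwards; it does not create a post-dose rule.
- Exclusions 15 and 16 are planning criteria. Treating their periods as times to avoid conception is an inference, though a fair one. A reader might go further and infer that those days carry known exposure risk. The documents do not support that: section 4.3 reports no significant accumulation, and 7.1.3 says only that fetal risk is unknown.
- A reader might infer that pregnancies go unreported. They do not: subject and partner pregnancies are notified and reported, and 12.8 puts no end date on this.
- A reader might infer that congenital anomalies would be lost to SAE reporting. That is not shown. The 7-day sentences say what will be collected and do not bar later reports. Section 13.1 asks for every ICH-defined SAE within 24 hours of awareness, 13.2 has no cut-off, and an anomaly could be found before birth. What remains is an ambiguity.
- Consent pages were removed before review and may give a contraception duration. The Pregnancy Reporting Form is not in the documents either, so its content is unknown. Even so, investigators apply 10.1 and 12.8, and a duration in the consent form would not supply partner follow-up.
- Partners are not trial subjects, so following them needs their own consent. This limits how the fix is worded, not whether it is needed.

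**Conclusion.** Two gaps are firm on the text: no post-dose contraception duration in inclusion 11, and no required outcome follow-up for partners of men on FSD201. The unclear SAE status of a congenital anomaly found at birth is secondary.

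The first gap covers 28 days for women and about three months for men at the widest reading, and at least 12 and 73 days at the narrowest considered. It applies only to women of childbearing potential and sexually active men among the 60 subjects; the documents do not give their share. Events should be rare. The day counts rest on the stated readings, and the birth intervals on assumed gestations. Efficacy, sample size and analysis are untouched. Severity: a minor safety wording change, worth making because the protocol's own stated reasoning calls for it.

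**What to change.** - **10.1 no. 11 and the matching synopsis criterion:** require contraception through 28 days (women) and three months (men) after the last dose, or the windows the sponsor confirms. Changing only one copy would make the protocol contradict itself.
- **12.8:** follow to outcome, with the partner's consent, pregnancies in partners of men on FSD201. Extend follow-up to pregnancies conceived within the post-dose windows.
- **12.8 and 7.1.3:** extend the pregnancy unblinding provision to those later pregnancies, or follow them regardless of arm until unblinding. Otherwise allocation may not be known before database lock.
- **13.1, 8.2.3 and 6.2:** add a sentence that congenital anomalies from followed pregnancies are reported as SAEs whenever they are identified.

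No visit or test is added, and any consent wording should be aligned. The costs are longer contraception for subjects, partner consent where a pregnancy occurs, and long contact for rare events: conception at the end of the men's window with a term birth means 92 + 266 = 358 days, about a year after the last dose.

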13.1. Reporting of Serious Adverse Events

All serious adverse events (SAE) defined per ICH guidelines must be recorded on case report forms. In addition, all serious adverse events must be reported, whether or not considered causally related to treatment using the SAE form to Ozmosis Research Inc. within 24 hours of becoming aware of the event. The SAE must be completely described in the case report form. The reporting period for SAEs is the period immediately following the time of first dose through the last follow-up visit. The investigator and/or Sponsor are responsible for informing the Ethics Committee and/or the Regulatory Authority of the SAE as per local requirements.

Serious Adverse Event Reporting Instructions

All serious adverse events must be reported as follows:

Within 24 hours: Report initial information (on trial specific SAE report form) by fax or e-mail to:

Ozmosis Research Inc.

Email: [contact]

[contact]

The initial information should always contain:

- Name of Reporter/Investigator

- Subject identification
- SAE Term
- Study drug dose and start/stop dates

On the next working day: Fax or e-mail completed trial-specific Serious Adverse Event form.

All SAEs must be followed until resolved, become chronic, or stable unless the subject is lost to follow up. Resolution status of such an event should be documented on the CRF.

13.2. Procedures for Expedited Reporting

Responsibility for Reporting Serious Adverse Events to Regulatory Authorities

Ozmosis Research Inc. will provide expedited reports SAEs to Intrinsik for submission to Health Canada and FDA according to applicable guidelines and regulations, i.e. events which are BOTH serious AND unexpected, AND which are thought to be related to protocol treatment (or for which a casual relationship with protocol treatment cannot be ruled out).

Reporting Serious Adverse Events to Local Ethics Boards

Ozmosis Research Inc. will notify all Investigators of all Serious Adverse Events that are reportable to regulatory authorities from this trial or from other clinical trials as reported to the Sponsor. This includes all serious events that are unexpected and related to protocol treatment. Investigators must notify their Research Ethics Board (REB) / Institutional Review Board (IRB) and file the report with their Investigator Site File. Documentation that serious adverse events (SAEs) have been reported to REB/IRB must be kept on file at Ozmosis Research Inc.

Documentation can be any of the following:

- Letter from REB/IRB acknowledging receipt
- Stamp from the REB/IRB, signed and dated by REB/IRB chair, acknowledging receipt
- Letter demonstrating the SAE was sent to the board

All expedited serious adverse events occurring within a centre should also be reported to local REB/IRB.

14. Statistical Methods and Planned Analyses

The intent-to-treat (ITT) population will consist of all randomized subjects. The safety population will include all randomized subjects who receive at least one dose of the study drug. The per-protocol population will consist of all subjects in the ITT population who have no major protocol deviations that would have a significant effect on the efficacy of the study treatment. The ITT

population will be the primary population for all efficacy analyses. All safety data will be summarized based on the safety population. The per-protocol population will be used as the population for sensitivity analyses of the primary and key secondary efficacy endpoints.

All efficacy and safety will be summarized descriptively.

14.1. Efficacy Analysis

As the primary analysis, the change from baseline in the weekly average of the daily pain intensity measured by NPRS will be analyzed using the mixed model for repeated measure (MMRM) with the treatment as a factor, visit, the interaction between treatment and visit, and baseline as a covariate. The analysis of covariance (ANCOVA) will also be used as an additional analysis. The change in the weekly average of the daily sleep score on Daily Sleep Interference Score (DSIS) and the change in the NPRS score will be analyzed using the same methods for primary endpoint analysis. The percentage of subjects achieving $\geq 30\%$ and $\geq 50\%$ reduction in NPRS score at Day 28 and Day 56 will be analyzed using Fisher's exact test and the logistic regression model. The change in Patient Global Impression of Change (PGIC) and other continuous efficacy endpoints will be analyzed using ANCOVA.

No multiplicity adjustment will be used in this study. The missing data imputation methods and sensitivity analyses for primary and key secondary efficacy endpoints will be included in Statistical Analysis Plan (SAP).

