10.5. Planned Sample Size

The planned sample size for this study is based on making a Go/No-Go evaluation, focussing on the percentage of patients achieving the reduction in NPRS score, that is, using the binary responder endpoint. A decision criterion is applied with possible decision outcomes being 'Go'

(suggests FSD201 warrants further development), ‘Stop’ (or no-Go, suggests further development of the FSD201 should stop), and ‘Pause’ (inconclusive, additional investigation should be performed before a decision is made). This decision framework was published by [Lalonde et al., \(2007\)](#) and [Frewer et al., \(2016\)](#). Note that these decision criteria will not be definitive as the final decision to continue development will be based on more than just the responder endpoint.

For this decision framework, a lower reference value (LRV) and a target value (TV) are defined for the treatment effect (i.e., difference in the drug response rate between FSD201 and placebo) as follows:

- LRV: The minimum treatment effect below which there is no desire to continue development the compound.
- TV: The targeted treatment effect above which the compound is expected to replace the current standard of care in terms of efficacy

The Go/No-Go calculations are based on the TV of a 30% difference between FSD201 and placebo, and the minimum difference to be considered for further development being 10% (LRV). Furthermore, the calculations have been made such that there is at most 30% probability of a false-go, i.e., there is at least 70% desired confidence that the treatment effect is better than a 10% improvement (LRV), given that a Go decision is made. Similarly, there is a maximum of 10% false-stop risk, i.e., a maximum probability that the treatment effect is better than a 30% improvement (TV), given a Stop decision is made. Finally, it is assumed that the placebo response rate is 20%.

2:1 randomisation

A total sample size of 60 patients (40 on FSD201 and 20 on placebo) has been chosen to balance the needs to minimize the probability of ‘Pause’ whilst maintaining reasonable recruitment cost and time. [Table 4](#) shows the probabilities of making a Go, Pause or Stop decision.

True Treatment Effect	Go	Pause	Stop
TV (30%)	85.2%	4.3%	10.4%
LRV (10%)	25.7%	7.5%	66.8%

Sum of the probabilities may not be 100% due to rounding for display

Table 4 Probabilities of Go, Pause or Stop Given the True Treatment Difference

11. Efficacy

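### At 40 v 20, Fisher's exact test for the secondary responder endpoints is needlessly conservative; an unconditional exact test gains about 6 points of power at the planning rates

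*Combined protocol and SAP*

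**What the plan says.** Section 14.1 (Efficacy Analysis) compares the proportions with ≥30% and ≥50% NPRS reduction at Day 28 and Day 56 using Fisher's "exact test and the logistic regression model". It states no significance level, no sidedness, no covariates or fitting method for the logistic model, no fallback for sparse cells, and no order of precedence between the two analyses. The same section makes an MMRM of change in NPRS the primary analysis and rules out multiplicity adjustment. The responder rates are secondary: ≥30% is in section 5.3.2 and ≥50% at Day 56 is in section 5.3.3.

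Section 10.5 (Planned Sample Size) bases the sample size on a Go/Pause/Stop evaluation, "focussing on the percentage of patients achieving the reduction in NPRS score, that is, using the binary responder endpoint". "A total sample size of 60 patients (40 on FSD201 and 20 on placebo) has been chosen", and "it is assumed that the placebo response rate is 20"%. "The Go/No-Go calculations are based on the TV of a 30% difference between FSD201 and placebo", with a lower reference value (LRV) of 10 points. The section adds that these criteria are not definitive. Table 4 gives the Go, Pause and Stop probabilities. No power is stated for Fisher's or any other test.

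**The concern.** Fisher's test conditions on the total number of responders. In a table as small and unbalanced as 40 v 20 the attainable p-values are coarse, so its true type I error sits well below the nominal level and power is lost with no gain in validity. An unconditional exact test keeps strict error control and recovers part of that loss.

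A second, smaller issue concerns the logistic model. If it is fitted by ordinary maximum likelihood (the text does not say), it has no finite treatment estimate when none of the 20 placebo patients responds. At stake is the precision of a secondary comparison on the type of endpoint that the sample-size section is built around.

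**Working it through.** **Inputs.** From section 10.5: 40 v 20, placebo rate 20%, target value (TV) 30 points (50% v 20%), LRV 10 points (30% v 20%), false-go risk 30%, false-stop risk 10%. Assumed: two-sided 5%.

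**1. The plan's own figure (Table 4).**
- SE at TV = √(0.5×0.5/40 + 0.2×0.8/20) = √0.01425 = 0.1194.
- SE at LRV = √(0.3×0.7/40 + 0.2×0.8/20) = √0.01325 = 0.1151.
- Raw cut-offs with the TV SE: 0.10 + 0.524×0.1194 = 0.163 for Go, and 0.30 − 1.282×0.1194 = 0.147 for Stop.
- Taken up to the next multiple of 1/40 (inferred, not stated): Go above 0.175, Stop below 0.15.
- True difference 30%: Go = Φ((0.30−0.175)/0.1194) = 85.2%; Stop = Φ((0.15−0.30)/0.1194) = 10.4%; Pause = 4.3%.
- True difference 10%: Go = 1−Φ((0.175−0.10)/0.1151) = 25.7%; Stop = Φ((0.15−0.10)/0.1151) = 66.8%; Pause = 7.5%.

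All six entries of Table 4 are reproduced, and no Fisher test is involved.

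**2. Fisher's test.** For a rejection region R among the 41 × 21 possible tables (x responders of 40, y of 20):
- Power = Σ over R of Bin(x; 40, p_T) × Bin(y; 20, p_C).
- Size = the same sum with p_T = p_C = π; maximum size is its largest value over π.

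With R = {Fisher two-sided p ≤ 0.05}, size is 3.5% at π = 20% and at most 3.7%. Power at 50% v 20% is 56.6%.

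**3. Boschloo's test.** This uses Fisher's two-sided p as the test statistic and refers it to its unconditional distribution: p_B = max over π of P(Fisher p ≤ observed Fisher p). At 5% it rejects when Fisher's p ≤ 0.0575. That region contains every table Fisher rejects plus 14 more, so this version is never less powerful. Maximum size is 4.9%. One added table is 19/40 v 4/20, with Fisher p = 0.051 and Boschloo p = 0.040.

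**4. Power across rates (two-sided 5%).**

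| FSD201 v placebo | Fisher | Boschloo | Gain (points) |
|---|---|---|---|
| 50% v 20% (planning rates) | 56.6% | 62.3% | 5.7 |
| 55% v 25% (assumed) | 53.0% | 60.5% | 7.5 |
| 60% v 30% (assumed) | 50.8% | 59.8% | 9.0 |
| 40% v 10% (assumed) | – | – | 0.8 |

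Barnard's test (pooled z) has 62.6% at the planning rates. At one-sided 2.5% and the planning rates, power is 53.1% for Fisher, 60.2% for Barnard and 63.2% for Boschloo, so the direction does not hang on the choice between these two levels.

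**5. The logistic model at 50% v 20%, unadjusted.** Power is 62.0% by the Wald test and 64.8% by likelihood ratio. Maximum size is 5.5% and 7.4% respectively, so it does not share Fisher's loss but is not strictly valid either.

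**6. No placebo responder.** The probability is (1−r)^20. At the stated 20% rate it is 0.8^20 = 1.2%. The ≥50% rate cannot exceed the ≥30% rate, but the documents give no figure for it. Assumed rates of 15%, 10% and 5% give 3.9%, 12.2% and 35.8%.

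**The case against.** The strongest reply is that Fisher's test is a valid, standard small-sample method. The responder rates are secondary to the MMRM, no alpha is stated, and so no documented decision turns on whether a responder p-value falls just above or just below 5%. That stands, and it limits how much weight the point can carry.

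Four stronger readings are tempting, and the documents do not support them.

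- *Both planned responder analyses give away power.* They do not: the logistic model's power at the planning rates is about equal to Boschloo's or higher.
- *The trial is under-sized because of Fisher's test.* Section 10.5 sizes by a rule on the difference in response rates. Changing the test alters no entry in Table 4.
- *A real effect would be missed under the plan.* Take 24/40 v 6/20, an observed 30-point difference. Fisher gives p = 0.054 and Boschloo 0.041 (0.035 in the doubled one-sided version). But the planned logistic model, unadjusted, gives 0.032 (Wald) or 0.027 (likelihood ratio). The plan would contain both answers and does not say which governs.
- *The logistic estimate is likely to be infinite.* At the only stated placebo rate the risk is 1.2%. The larger figures rest on assumed rates for the ≥50% endpoint, and Fisher's test would still return a valid p-value in that case.

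What survives is that a strictly valid test with more power is available at almost no cost.

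**Conclusion.** The point holds in a limited form. At 40 v 20 and an assumed two-sided 5%, Fisher's test is more conservative than it needs to be: maximum size 3.7% against 4.9% for Boschloo. At the plan's own rates this costs 62.3 − 56.6 = 5.7 points of power. The size of the gain depends on response rates that are not known in advance. The 9.0-point figure rests on a 30% placebo rate that the plan does not use, and the gain nearly vanishes at a 10% placebo rate. The sparse-cell problem is minor at the stated 20% rate and could matter for the ≥50% endpoint if its placebo rate is low. Neither issue touches the primary analysis, the sample size or the Go/Pause/Stop probabilities. This is an improvement to consider, not a flaw that threatens the trial's conclusions.

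**What to change.** In section 14.1:

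- Replace Fisher's exact test with Boschloo's (or Barnard's) unconditional exact test, and name it as the governing test for the responder comparisons.
- State alpha, sidedness and the version used. The version matters, because the two-sided-ordering and doubled one-sided forms of Boschloo's test give different p-values.
- Specify the logistic model as supporting, with baseline average NPRS as a covariate (14.1 already adjusts the MMRM for baseline) and Firth penalisation, so that the estimate stays finite if no placebo patient responds.

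The cost is analysis-plan wording and available software options, with no added patients or procedures. The downside is a less familiar test and slightly more computation.
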